9.3. Definition of Adverse Drug Reaction (ADR)

This is defined as any noxious and unintended (harmful or unwanted) response to a medicinal product normally used in man for prophylaxis, diagnosis or therapy of diseases, or for modifications of physiological function, and is suspected to be related to the drug. A suspected ADR is fulfilled, if the causality is judged as possible or probable by the investigator.

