6.2. Sorafenib/placebo - dose modifications and delays

Sorafenib/placebo therapy will be taken according to defined dose levels:

Dose level 1 (starting dose) : 2 tablets / day (1-0-1)
 Dose level 2 (escalated dose): 3 tablets / day (1-0-2)
 Dose level 3 (targeted dose) : 4 tablets / day (2-0-2)

The starting dose will be dose level 1 in order to allow adaption to the drug and avoid acute toxicities. If after the run-in phase of 2 weeks dose level 1 was well tolerated (no probably related AE's > grade 1), the next dose level (dose level 2) will be commenced and maintained for the next 4 weeks. If, after this time, dose level 2 was well tolerated the targeted standard dose level (dose level 3) will be administered indefinitely. Dose level 3 is the targeted dose.

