6.2.1. Dose delay and modifications for non-hematological toxicity

In case of severe toxicities, dose reductions or delays will be required as specified in Table 2. It illustrates dose modifications for all non-hematologic toxicities according to CTCAE Version 4.02 in the CRF, except for skin toxicities, which will be detailed separately below. These recommendations pertain, if the adverse event is considered related to sorafenib.

Table 2: Non-hematologic criteria for dose delay and dose modification of sorafenib (except skin toxicity)^a

Grade	Dose Delay	Dose modification
0-2	none	No change
3	Interrupt until \leq grade 2 ^b	Resume with one dose level below last dose level ^c
4	OFF protocol therapy	OFF protocol therapy

a. Excludes nausea/vomiting that has not been pre-medicated, and diarrhea.

b. If no recovery within an up to 28-day delay, treatment will be permanently terminated unless the patient is deriving clinical benefit

c. The dose of study drug may be increased from the reduced dose level stepwise every 4 weeks to dose level 3 if tolerated (no re-appearance of non-hematological toxicity \geq grade 0-2). In case toxicity recurs, and repeated dose reductions are required (more than 2), treatment will be indefinitely performed with dose level 1. When this is also not tolerated study treatment will be permanently discontinued.

For the purpose of dose modifications, patients experiencing Hand-Foot syndrome should have their signs and symptoms graded according to the following system (see below). Other skin toxicities will be graded according to CTCAE Version 4.02.

- Grading for Hand-Foot Syndrome

Grade 1

Numbness, dysesthesia/paresthesia, tingling, painless swelling or erythema of the hands and/or feet and/or discomfort, which does not disrupt normal activities.

Grade 2

Painful erythema and swelling of the hands and/or feet and/or discomfort affecting the patient's activities.

Grade 3

Moist desquamation, ulceration, blistering or severe pain of the hands and/or feet and/or severe discomfort, which cause the patient to be unable to work or perform activities of daily living.

According to the grade and incidence of skin toxicity (including rash and hand-foot syndrome) for a given patient, the following dose modification schedule will be followed (see Table 3).

Table 3: Skin Toxicity Criteria for Dose Modification of Sorafenib

Toxicity Grade	Dose modification	Dose level after interruption

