9.5. Definition of Suspected Unexpected Serious Adverse Drug Reaction

The definition of a SUSAR is a serious adverse drug reaction or Serious Adverse Events related to Sorafenib, the nature or severity of which is not consistent with the applicable product information and therefore is considered “unexpected” with regard to the valid Summary of Product Characteristics for Sorafenib.

A serious event or drug reaction is not defined as a SUSAR when:

- a) It is serious, but expected;
- b) It does not fit the definition of a SAE or SADR, whether expected or not.

10. Recording, reporting and reviewing

It is the investigators responsibility to maintain an accurate and up to date record of all adverse events/occurrences in patients participating in the clinical trial. This record, including details of nature, onset duration, severity, outcome and any relationship to investigational product, should be made on the relevant documentation as specified below. Medical terminology according to CTCAE Version 4.02 should always be used to describe any event. Investigators should avoid vague terms such as “sick”. For details on assessing causality, see section 10.4 below.

It is the investigators responsibility to review all events occurring at their site and as such, the investigator must ensure that the patients are not compromised. Any appropriate action must be taken to protect the patients whilst ensuring validity of the results.

10.1. *Reporting of Adverse Events*

Adverse events will be reported on CRFs from the time the informed consent is signed, up to and including 30 days following last administration of study drug. In case that a patient has an open AE at the end of the study, it has to be reported until the AE is resolved or got the status unresolvable or the data base is closed. If the patient needs a therapy different from the clinical trial for treatment of the same indication, the reporting of the AE ends at the beginning of this therapy.

The severity of AEs will be graded according to the National Cancer Institute Common Terminology Criteria for AEs (CTCAE) 4.02 for Cancer Clinical Trials.

10.2. *Reporting of Serious Adverse Events*

All SAEs have to be recorded from the time the informed consent is signed, up to and including 30 days following last administration of study drug on the appropriate SAE pages in the CRF. Ongoing SAEs have to be reported every four weeks.

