10.4. Assessment of causality of adverse events / reactions

The relationship of adverse events to the medicinal products being studied should be determined according to the classification below:

certain:

- Event or laboratory test abnormality, with plausible time relationship to drug intake
- Cannot be explained by disease or other drugs
- Response to withdrawal plausible (pharmacologically, pathologically)
- Event definitive pharmacologically or phenomenologically (i.e. an objective and specific medical disorder or a recognized pharmacological phenomenon)
- Rechallenge satisfactory, if necessary

probable:

- Event or laboratory test abnormality, with reasonable time relationship to drug intake
- Unlikely to be attributed to disease or other drugs
- Response to withdrawal clinically reasonable
- Rechallenge not required

possible:

- Event or laboratory test abnormality, with reasonable time relationship to drug intake
- Could also be explained by disease or other drugs
- Information on drug withdrawal may be lacking or unclear

unlikely:

- Event or laboratory test abnormality, with a time to drug intake that makes a relationship improbable (but not impossible)
- Disease or other drugs provide plausible explanations

not related:

- no causal relationship

not assessable:

- Report suggesting an adverse reaction
- Cannot be judged because information is insufficient or contradictory
- Data cannot be supplemented or verified

not applicable:

- If any of causal relationship does not make sense (e. g. exposure during pregnancy, overdose, medication error)

unknown:

- no information is available

11. *Statistical Considerations*

11.1. *Description of analysis sets*

Intention to treat set (ITT)

The ITT set includes all patients who were randomized regardless of whether they received treatment or not. Patients will be analysed in the treatment group they were randomized to, regardless of whether they were treated in this group or not.

Per-protocol set (PP)

The PP set includes the patients of the corresponding ITT-set for whom no major protocol violations occurred. A compilation of the major protocol deviations will be generated by the coordinating investigator.

Safety Set

The safety set of the study consists of patients who received at least one dose of sorafenib or placebo and for whom post-dose data are available. Patients will be analysed in the

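### Events rated *certain* on the protocol's causality scale fall, as written, outside both the suspected-ADR definition and the run-in tolerability rule

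*Protocol*

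**What the plan says.** Protocol section 10.4 sets one scale for all events: "The relationship of adverse events to the medicinal products being studied should be determined according to the classification below". It has eight categories: certain, probable, possible, unlikely, not related, not assessable, not applicable and unknown. The top two are kept apart by their criteria. *Certain* requires, among other things, "Cannot be explained by disease or other drugs", while *probable* requires "Unlikely to be attributed to disease or other drugs".

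Four other places turn this scale, or an undefined notion of relatedness, into a rule:

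- Section 9.3 first describes an ADR as a response that "is suspected to be related to the drug", and then gives the test: "A suspected ADR is fulfilled, if the causality is judged as possible or probable by the investigator". Section 9.4 defines a serious ADR as an ADR that is serious.
- Section 6.2 allows escalation after the run-in if "dose level 1 was well tolerated (no probably related AE's > grade 1").
- Section 6.2.1 introduces the non-haematological dose-modification table with "These recommendations pertain, if the adverse event is considered related to sorafenib".
- Section 9.5 defines a SUSAR as an unexpected "serious adverse drug reaction or Serious Adverse Events related to Sorafenib".

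The protocol nowhere says that *probable* means at least probable, and nowhere states which categories of section 10.4 make an event *related*.

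**The concern.** A causality threshold should be monotone: if an event counts at one level of evidence, it should also count at a higher level. Sections 9.3 and 6.2 break this at the top of the scale. An investigator who has to choose between *probable* and *certain* takes the event out of the literal ADR set, and out of the literal run-in rule, by choosing the stronger rating.

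Two things are at stake. One is whether the ADR and SADR labels are correct if they are assigned, or derived by program, from the recorded category. The other is whether the tolerability rule is applied in the same way across the 10 to 20 centres foreseen in section 5, because each centre would have to supply its own mapping.

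**Working it through.** The protocol gives no figure on this point, so the check sets the rules side by side. Inputs are the section 10.4 categories that express a suspected causal link, and the wording of sections 9.3, 9.4, 6.2, 6.2.1 and 9.5.

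| Rating (10.4) | Suspected ADR (9.3) and SADR if serious (9.4) | Defeats tolerability of dose level 1 if above grade 1 (6.2) | *Related* for Table 2 (6.2.1) | *Related* SAE in the SUSAR definition (9.5) |
|---|---|---|---|---|
| certain | not named | not named | category not stated | category not stated |
| probable | named | named | category not stated | category not stated |
| possible | named | not named | category not stated | category not stated |

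**Step 1, the ADR definition.** The named set is {probable, possible}. *Certain* is missing, and section 9.4 inherits the gap.

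**Step 2, the run-in rule.** The named set is {probable}. Take a grade 2 event in the first two weeks that is neither a skin event nor haematological nor hypertension. Rated *probable*, it defeats tolerability. Rated *certain*, it does not, if the words are followed. Table 2 leaves the dose unchanged for grades 0 to 2, so it does not close the gap.

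**Step 3, how far other rules cover the gap in section 6.2.**
- Table 2 acts on related grade 3 and grade 4 non-haematological events.
- Table 3 acts on grade 2 and grade 3 skin events.
- Table 4 acts on symptomatic or persistent grade 2 hypertension and on higher grades.
- Table 5 acts on grade 3 and grade 4 haematological toxicity.

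What remains is mainly the other grade 2 events.

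**Step 4, where the ADR label is used.**
- Sections 11.3 and 11.4 compare numbers of adverse events between arms by Fisher's exact test, with no causality filter.
- Section 9.2 defines an SAE regardless of causality.
- Sections 10.1 to 10.3 set reporting duties for AEs, SAEs and SUSARs, and none for ADRs or SADRs as such.
- Section 13.1 gives the safety committee SAEs and SUSARs to review.
- Section 10.2 has the Principal Investigator review each SAE again for relatedness.
- Section 9.5 admits related SAEs beside SADRs, so a serious unexpected event rated *certain* can still become a SUSAR.

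The ADR definition therefore feeds section 9.4 and one of the two routes in section 9.5. No planned analysis uses it.

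**The case against.** The strongest reply is that section 9.3 gives a sufficient condition, not an exclusive one, and that its first sentence, on a suspected relation to the drug, covers *certain* all the more. A sensible investigator would include such events. This largely stands as a reading of intent. It does not remove the problem, because the second sentence is the operational test that a program deriving a flag would follow. Section 6.2 has no broader sentence to fall back on.

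It can also be said that *certain* will be rare. The trial is double-blind, patients take interacting drugs after transplantation, and GvHD is a stated alternative explanation for diarrhoea. Recurrence on resuming treatment is not enough for the rating, since the other criteria in section 10.4 must also be met. This is fair. The documents give no frequency, so no share of affected events can be stated.

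Finally, different thresholds for escalation, dose modification and ADR labelling may serve different purposes. In particular, counting *possible* for an ADR but not for run-in tolerability may be deliberate and is not treated here as an error. The omission of *certain* is different, because a threshold that drops its strongest category is hard to explain by purpose.

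A reader might go further and infer that the toxicity comparison of sorafenib with placebo would be biased, or that SAEs and SUSARs would be lost. The documents do not support either. No ADR or SADR count is planned, the planned comparison uses all adverse events, SAEs are recorded whatever their cause, and SUSARs have the second route. Nor can it be inferred that higher-grade events rated *certain* would generally be escalated through, since Tables 2 to 5 act on many of them.

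**Conclusion.** The inconsistency is real and minor. Of the three section 10.4 categories that express a suspected causal link, the strongest is absent from the ADR definition and from the run-in rule, and sections 6.2.1 and 9.5 use *related* without naming categories. The effect is confined to ADR and SADR labelling and to uniform application of the run-in rule, mainly for grade 2 events outside Tables 2 to 5. SUSAR reporting is not lost, although its second route rests on an undefined word.

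The conclusion assumes that the rules are followed as written. If every centre reads *probable* as at least probable, nothing changes in practice, but the protocol does not say so.

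**What to change.** In section 9.3, define a suspected ADR as causality rated *certain*, *probable* or *possible*. Section 9.4 then follows without change. In section 9.5, state that *related* means the same three categories.

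Reconcile sections 6.2 and 6.2.1 with section 10.4, so that each rule names the categories that count. Which categories should govern escalation or dose modification is a clinical decision for the sponsor. If the different handling of *possible* is intended, say so.

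The cost is a wording amendment of a few sentences and, at most, a change to how an ADR flag is derived. No new data, visits or sample size are needed. The number of events labelled as ADRs may rise slightly.

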9.4. Definition of Serious Adverse Drug Reaction (SADR)

This is defined as an adverse drug reaction (ADR) that is serious (see SAE criteria above).

9.5. Definition of Suspected Unexpected Serious Adverse Drug Reaction

The definition of a SUSAR is a serious adverse drug reaction or Serious Adverse Events related to Sorafenib, the nature or severity of which is not consistent with the applicable product information and therefore is considered “unexpected” with regard to the valid Summary of Product Characteristics for Sorafenib.

A serious event or drug reaction is not defined as a SUSAR when:

- a) It is serious, but expected;
- b) It does not fit the definition of a SAE or SADR, whether expected or not.

10. Recording, reporting and reviewing

It is the investigators responsibility to maintain an accurate and up to date record of all adverse events/occurrences in patients participating in the clinical trial. This record, including details of nature, onset duration, severity, outcome and any relationship to investigational product, should be made on the relevant documentation as specified below. Medical terminology according to CTCAE Version 4.02 should always be used to describe any event. Investigators should avoid vague terms such as “sick”. For details on assessing causality, see section 10.4 below.

It is the investigators responsibility to review all events occurring at their site and as such, the investigator must ensure that the patients are not compromised. Any appropriate action must be taken to protect the patients whilst ensuring validity of the results.

10.1. *Reporting of Adverse Events*

Adverse events will be reported on CRFs from the time the informed consent is signed, up to and including 30 days following last administration of study drug. In case that a patient has an open AE at the end of the study, it has to be reported until the AE is resolved or got the status unresolvable or the data base is closed. If the patient needs a therapy different from the clinical trial for treatment of the same indication, the reporting of the AE ends at the beginning of this therapy.

The severity of AEs will be graded according to the National Cancer Institute Common Terminology Criteria for AEs (CTCAE) 4.02 for Cancer Clinical Trials.

10.2. *Reporting of Serious Adverse Events*

All SAEs have to be recorded from the time the informed consent is signed, up to and including 30 days following last administration of study drug on the appropriate SAE pages in the CRF. Ongoing SAEs have to be reported every four weeks.

The Investigator must fax or E-mail all serious adverse events (SAEs) to the KKS within 1 working day after awareness of the event. Where possible, a diagnosis rather than a list of symptoms should be given. The Investigator should complete all the details requested including dates of onset, severity, corrective therapies given, outcome and opinion as to whether the adverse event is likely to be drug-related. The Investigator should not wait for full details before making the initial report. Personal data have to be replaced by the trial patient number before forwarding any information.

If the event is fatal or life threatening, the Investigator must fax any relevant follow-up information of the reported SAE to the KKS within additional 8 days. If the reported SAE is not fatal or life threatening, the investigator must fax follow-up information as soon as possible.

In case of death, the Investigator has to supply Principal investigator, KKS, Competent Authority and Ethics Committee with all details requested.

The Principal Investigator will review the SAE again for seriousness and relatedness and assess the SAE for expectedness according to Summary of Product Characteristics (Product Information) or Investigator's Brochure as applicable.

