6.7.2. Discontinuation

In case of relapse the primary endpoint of this study is reached and study medication has to be stopped immediately.

Treatment of relapse will be left to the discretion of the treating investigator. Investigators should note that sorafenib should not be given after relapse.

7. Study procedures

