11.2. Power and Sample Size Calculation

The primary endpoint of the study, relapse-free survival (RFS), is defined as the time interval from randomization until relapse or death from any cause, whichever occurs first. For a patient with none of these events before the end of study follow-up, observation of RFS will be censored at the date of his or her last follow-up examination. It is assumed that the RFS rate after 2 years may be increased from 65% with placebo (Gale et al., Blood 2005; Thiede et al., Blood 2006) to 82.5% with sorafenib, corresponding to a hazard ratio (HR) of 0.45. Comparing the sorafenib with the placebo group by a log-rank test at a two-sided alpha of 5%, 49 observed events are required to obtain a power of 80%. It is important to note that due to a decreasing likelihood of relapses over time, the Kaplan-Meier curve for RFS of Flt3-ITD AML patients after allo-SCT forms a plateau after around 2 years at the above-mentioned values.

Under these assumptions, 184 patients (i.e., 92 per group) are needed in order to observe 49 events after a minimum observation period of 24 months for each patient. The inclusion of a total of 200 patients in the study allows for compensation of a dropout rate of 8%. During the course of the study, it may be decided to adapt the number of included patients. If this is done based on a data inspection (rather than solely on the absolute number of events which occurred so far, irrespective of the study arm), the method for sample-size adaptation in survival trials developed by Schäfer and Müller (Schäfer H, Müller H-H. Modification of the sample size and the schedule of interim analyses in survival trials based on data inspections. Statist Med 2001;20:3741-3751) will be employed which ensures that the type I error risk is not affected. It may also be decided later to add one or more interim analyses using the adaptive method mentioned above, especially if the sample size is increased.

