observation of OS will be censored on the date the patient was last known to be alive. This and other secondary objectives will be analyzed by the Kaplan-Meier method and the log-rank test. Furthermore, RFS and OS will be analyzed by Cox regression in order to account for prognostic factors (Flt3-ITD ratio at diagnosis, treatment with Flt3-inhibitors before allogenic stem cell transplantation, occurrence of chronic GvH). The analysis will be performed according to the intention-to-treat principle.

With regard to safety, numbers of adverse events will be analyzed descriptively as well as in comparison between the two study arms by means of Fisher's exact test.

12. Efficacy

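### Adverse-event recording closes a fixed time after the last dose and relapse forces the last dose, so time at risk may differ by arm; the Fisher's exact comparison in 11.4 cannot allow for that

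*Protocol*

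**What the plan says.** Comparing the toxicity of sorafenib maintenance with placebo is a secondary objective (Protocol 4.1.2). Four parts of the protocol decide how long AEs are collected and how the arms are compared.

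- **Recording window, text.** Sections 10.1 and 10.2 collect AEs and SAEs from consent "up to and including 30 days following last administration of study drug". After a sentence on AEs still open at the end of the study, 10.1 adds "If the patient needs a therapy different from the clinical trial for treatment of the same indication, the reporting of the AE ends" at the start of that therapy.
- **Recording window, Table 6.** The schedule records AEs continuously to the end of study. A footnote sets that at six months after last protocol treatment and applies the assessment also to patients who stop for relapse.
- **Treatment stop.** Section 6.7.2: "In case of relapse the primary endpoint of this study is reached and study medication has to be stopped immediately". Without relapse, treatment runs 24 months (7.1.3).
- **Analysis.** Section 11.4: "numbers of adverse events will be analyzed descriptively as well as in comparison between the two study arms by means of Fisher's exact test". Section 11.3 names the same test for the early safety look.

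The relapse figures are in 11.2: "It is assumed that the RFS rate after 2 years may be increased from 65% with placebo" "to 82.5% with sorafenib, corresponding to a hazard ratio (HR) of 0.45". The same section says that relapses become less likely over time and that the RFS curve flattens at around two years.

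**The concern.** The window has the same wording in both arms, but its end is tied to the last dose, and relapse forces the last dose. If sorafenib prevents relapse, its patients stay on drug and under AE observation longer. They then collect more events even if the drug adds no hazard, so part of the efficacy would be read as toxicity. If sorafenib patients instead stop more often for other reasons, their window closes earlier and later harms are under-counted in that arm. A crude comparison of proportions cannot separate either effect from true toxicity.

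**Working it through.** **1. The plan's own figures.** HR = ln(0.825)/ln(0.65) = 0.447. The plan states "49 observed events are required to obtain a power of 80"% for the log-rank test at two-sided 5%. Schoenfeld's formula gives 4 × (1.960 + 0.842)² / (ln 0.447)² = 4 × 7.849 / 0.650 = 48.3, so 49 events. Expected events in 184 patients: 92 × 0.35 + 92 × 0.175 = 48.3. Allowing for dropout: 184 / 0.92 = 200. The plan's figures reproduce.

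**2. Mean AE observation time.** Take the time to RFS event or month 24, plus a tail of x months: x = 1 for 10.1 (30 days) and x = 6 for Table 6. With constant hazard, λ = −ln(S₂₄)/24, which is 0.01795 (placebo) and 0.00802 (sorafenib) per month. The mean time to event or month 24 is (1 − e^(−24λ))/λ: 0.35/0.01795 = 19.50 months and 0.175/0.00802 = 21.83 months. For the falling hazard described in 11.2, I assume a Weibull curve of shape 0.5 with the same 24-month rates. The integral of exp{ln(S₂₄)·(t/24)^0.5} gives 18.10 and 21.13 months.

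| Window | Hazard | Placebo | Sorafenib | Placebo shortfall |
|---|---|---|---|---|
| 10.1 (+1 month) | constant | 20.50 | 22.83 | 10.2% |
| 10.1 (+1 month) | shape 0.5 | 19.10 | 22.13 | 13.7% |
| Table 6 (+6 months) | constant | 25.50 | 27.83 | 8.4% |
| Table 6 (+6 months) | shape 0.5 | 24.10 | 27.13 | 11.2% |

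The tail is credited to every RFS event, including deaths, which have none, so these shortfalls are slightly low.

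**3. Effect on the share of patients affected.** Let the AE hazard μ be equal in both arms (an assumption; the protocol gives no AE rates). With constant λ, the share with at least one AE is 1 − e^(−μx)·[λ/(λ+μ)·(1 − e^(−24(λ+μ))) + e^(−24(λ+μ))]. For μ = 0.05 and x = 1:

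- Placebo: 1 − 0.951 × (0.264 × 0.804 + 0.196) = 61.2%.
- Sorafenib: 1 − 0.951 × (0.138 × 0.752 + 0.248) = 66.5%.

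The shape 0.5 values come from numerical integration.

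| AE hazard | Window | Constant: placebo vs sorafenib | Shift | Shape 0.5: placebo vs sorafenib | Shift |
|---|---|---|---|---|---|
| 1%/month | 10.1 | 18.31% vs 20.29% | 2.0 | 17.04% vs 19.65% | 2.6 |
| 5%/month | 10.1 | 61.17% vs 66.49% | 5.3 | 56.80% vs 64.33% | 7.5 |
| 5%/month | Table 6 | 69.76% vs 73.90% | 4.1 | 66.35% vs 72.22% | 5.9 |

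At 100 per arm, under the constant-hazard 10.1 case, the chance that Fisher's test gives p ≤ 0.05 is 4.4% at 1%/month and 9.3% at 5%/month, against about 3% at equal exposure. If events rather than patients are counted, the expected ratio is the observation ratio, 22.83/20.50 = 1.11.

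**4. What would cancel it.** With constant hazards, equal exposure needs an extra stopping hazard on sorafenib of 0.01795 − 0.00802 = 0.00993 per month. By month 24 that is 1 − 0.65/0.825 = 21% of patients. More than that reverses the sign.

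**5. Which methods remove it.** With constant μ, patients with a first event divided by months to first event or window close has expectation μ in both arms, so the rate ratio is 1. Cumulative incidence with relapse, death and drug stop as competing events equals the crude proportion when follow-up is otherwise complete. It would show the same differences as in step 3.

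**The case against.** **The stronger reading.** A reader might infer from 10.1 that all AE recording stops at relapse or at new anti-leukaemic therapy. The documents do not support this. The sentence follows one about an AE still open at the end of the study and speaks of that AE. The general rule is last dose plus 30 days, 5.8 asks for a safety assessment about one month after the last dose, and Table 6 runs longer. A reader might also infer that the comparison is known to be biased against sorafenib. The protocol gives no discontinuation rates by arm, so the net direction is not known.

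**Size and relevance.** The shift is modest, is small for uncommon AEs, and hardly touches AEs of the first weeks. Section 11.3 reports only 45 patients randomized after 40 months; in a smaller trial a few points are hard to tell from chance. No decision rule depends on this p-value, and the crude proportion is a legitimate description of harm experienced under each strategy. All of this stands. The expected shift in proportions, however, does not shrink with sample size, and it is what a reader of the safety table sees.

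**GvHD.** Chronic GvHD is a weak example of a missed late harm, because section 4 documents GvHD on a separate chart.

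**Place.** Exposure-adjusted rates are a usual SAP addition, and 11.4 does not exclude them. But the point is not an omission: the protocol itself names a between-arm test that does not suit its own recording window.

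**Conclusion.** The point holds in a limited form. AE observation depends on the efficacy outcome under both windows the protocol gives, and those two windows contradict each other. On the plan's RFS rates, counting RFS events only, placebo patients are observed about 10% to 14% less (10.1) or 8% to 11% less (Table 6). With equal AE hazards, the share affected shifts against sorafenib by 2.0 to 2.6 points at 1%/month and 5 to 8 points at 5%/month under 10.1, or 4 to 6 points at 5%/month under Table 6. It matters mainly for common or late AEs.

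The RFS rates come from the protocol. The Weibull shape and the AE hazards are assumptions, as is the absence of other drug stops. About 21% extra stops on sorafenib would cancel the effect in the constant-hazard case. An unknown sign is itself a reason to account for time at risk.

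**What to change.** In 11.4, base the between-arm AE comparison on time at risk. For each AE term and grade group, report patients with a first event per patient-month of AE observation. Compare arms by rate ratio or cause-specific hazard ratio, with observation ending when the AE window closes. The hazard ratio is preferable where the AE rate changes over time.

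Keep Fisher's exact test, applied to patients rather than event counts, for an early common window such as the first 3 months, or as a crude descriptive comparison. Cumulative incidence with competing events may be shown descriptively, with a note that it does not remove the artefact. Reconcile the AE window in 10.1 and 10.2 with Table 6, so that the denominator is defined once.

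The cost is wording in 11.4 and in the window definition, plus a little programming. AE onset is already recorded (section 10), and RFS event dates are needed for the primary endpoint. The downside is a slightly less simple safety table.
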